H4: Behavior: We hypothesize that Active vs Sham CES will lead to increased performance on tasks typically degraded by stress exposure, including a recognition memory test and a spatial memory test.

3.0 Participant Population:

We expect to recruit up to 500 individuals, including Soldiers and civilians, to achieve a final sample size of 40 complete data sets. Our high recruitment number allows for Soldier group briefings (active-duty units at their home station and HRV cohorts at DEVCOM SC) which are routinely 30+ and can be upwards of 100 Soldiers.

We anticipate an approximately 40-50% attrition rate given our requirement to meet a minimum CES threshold of $300\mu\text{A}$ (i.e., a $250\mu\text{A}$ minimum CES intensity) and the prolonged study duration. To accommodate the potentially high attrition rate, we expect to recruit and consent up to 500 Soldiers and/or civilians, and schedule and enroll up to 100 Soldiers and/or civilians.

We are recruiting civilians in addition to military personnel because we have limited access to military personnel to conduct this research, and we have no a priori reason to believe that civilians will show markedly different stress responses, task performance, or CES responses relative to military personnel. In fact, most extant research examining the utility of CES for stress reduction is conducted with civilians. Because one of our tasks (marksmanship) could be considered geared towards military personnel, see

Section 15 for a description of possibly increased risk of psychological harm to civilians versus military personnel.

We will recruit participants 18-40 years of age, or 17 years if emancipated minor. This age range was chosen to represent the majority of Active Duty enlisted military personnel, which is under 41 years of age (*Defense, 2014*). There is no gender-based enrollment restriction.

Inclusion Criteria: Eligible individuals include those who:

1. Can sit and stand freely.
2. Have not used or experienced CES administration in the past.
3. Agree to have their data stored in a repository (database) for future use. Peer-reviewed scientific journal may require data to be stored in a repository as a condition for publication. Such repositories are online databases, in which coded data is linked (no link to participants personally) to the journal article citation.

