5.2 Sample Size

Sample size estimation was based on effect sizes from Barclay & Barclay (2014) who found that CES reduced subjective anxiety with an effect size of $f = 0.47$. Using GPower, the total sample size was estimated to be 38 to achieve power of 0.80 with an alpha criterion of 0.05. Our goal is therefore 40 complete data sets, with 20 participants in each of the two groups.

6.0 Procedures Involved:

We will use a double-blind, placebo-controlled design with random assignment of participants to one of two experimental groups: Active versus Sham CES. Two versions of the critical learning and virtual reality tasks have been developed (Brunyé & Giles, 2023; used in DEVCOM Armament Center IRB protocol 18-007, Tufts University protocol 1808016), and will be used herein, in balanced order across participants.

Military participants will be transported to and from the CABCS research performance site in Medford, MA, for participating in the baseline and follow-up session. If overnight accommodations are required for Soldiers, those will be provided along with other travel related items (e.g., per diem). Travel will be planned by the research team and coordinated with unit leadership (if troop request) or HRVPO (if HRVs). Civilian participants will not be provided with transportation, accommodations, or any other travel-related compensation.

All non-disposable devices used in the protocol will be disinfected in accordance with Occupational Health and Safety Administration and Centers for Disease Control

guidance, and product label instructions, paying attention to the required personal protective equipment and the contact time needed to achieve disinfection. In addition, all frequently touched surfaces in the research area, such as workstations, countertops, and doorknobs will be cleaned between participants.

Upon scheduling, participants will be randomly assigned to the Active or Sham CES condition, using the [=rand()] function in Microsoft Excel. All participants will complete a Thresholding & Baseline session, the CES administration sessions, and then a Follow-up session.

Testing Day 1: Thresholding & Baseline

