The final testing day will serve as the follow-up session to assess whether 20 sessions of Active (versus Sham) CES will impart any changes to the biochemical, physiological, affective, or behavioral responses to stress induction. This session will be held at approximately the same time of day as the thresholding and baselining session, within 5 days of the last daily CES session. The procedures for this session will precisely match the thresholding and baselining session but without the thresholding phase. After completing the final testing day, participants will have completed the study.

Data Analysis

We will analyze data from our biochemical, physiological, affective, and behavioral measures using Generalized Estimating Equations (GEEs) and/or Analyses of Variance (ANOVAs) to examine changes over the 20 CES sessions, changes from baseline to follow-up, and changes due to Active versus Sham CES. An effect will be deemed statistically significant if the likelihood of its occurrence by chance is $p < 0.05$; to reduce the likelihood of a Type I error, any follow-up comparisons (e.g., t-tests) will use a Bonferroni-corrected alpha criterion.

6.1 Additional Safeguards for Special Populations:

This research is funded by the Department of Defense, and the funding agency is interested in how military personnel respond to CES administration; for that reason, we will prioritize the recruitment of military personnel, and secondarily recruit from civilian populations as required to fulfill our sample size goal.

When recruiting military personnel to participate in this research, we will conform to additional safeguards for the protection of human subjects outlined in DoD Instruction (DoDI) 3216.02. These include additional safeguards to protect participants who may be more vulnerable to coercion or undue influence.

7.0 Investigational Medical Devices:

For the CES sessions, we will be using the Alpha-Stim AID cranial electrotherapy stimulator (CES) medical device, which is an FDA cleared, handheld medical device used for the treatment of anxiety, insomnia, and depression (i.e., AID; see Appendix D).

Because our study is using the device with healthy participants, the device is being used off-label in a manner that is for *investigational use only*. As detailed in the Informed Consent Form, this means that the device is being used in a study examining its safety or effectiveness, and not for the treatment, diagnosis, or prevention of any disorder.

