Cranial Electrotherapy Stimulation on Acute Stress

NCT06034496

May 8, 2025

Statistical Analysis Plan (SAP)

Manipulation Check. To ensure effective stress induction, we will assess AA, HR, CORT, and subjective stress responses to stress exposure during the baseline session. We will compare sampled AA levels from immediately prior to (pre) to immediately after stress exposure (i.e., time points pre and 0-min post-task). We will compare mean HR from immediately prior to (pre) to during stress exposure (i.e., during the RMT, SOT, DMT). We will compare sampled CORT levels from immediately prior to (pre) to 0-minutes after stress exposure (i.e., time points pre and 0-min post-task). We will compare STAI-S scores from immediately prior to (pre) to immediately after stress exposure. For these analyses, we will conduct paired t-tests.

Physiological & Biochemical Responses to CES. To evaluate physiological and biochemical responses to CES, we will use analysis of variance (ANOVA)s to assess the effect of CES Group (2: Active, Sham), Session (2: Baseline, Follow-up), and Time (pre-task, 0-min, 20-min, 40-min, 60-min post-task) on each of six outcome measures: HR, HRV, RR, tonic PD, AA, and CORT (number of levels varies as a function of outcome measure and is described as follows). Each response measure will be assessed in a discretized time series based on its sampling times; continuous measures (e.g., HR) will be discretized into pre-stress versus during-stress time periods. For HR, HRV, respiration, and tonic PD, pre-stress will be calculated as the mean of the one-minute time period immediately preceding the beginning of the tasks, and during-stress will be calculated as the mean of the entire behavioral task performance. For AA and CORT, we will include all five time points in the analysis (i.e., pre-task, 0-min, 20-min, 40-min, 60-min post-task).

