Cognitive & Affective Responses to CES. To evaluate the cognitive and affective responses to CES, we will use mixed ANOVAs to assess the effect of CES Group (2: Active, Sham) and Session (2: Baseline, Follow-up) on each of four cognitive outcome measures, and one affective outcome measure. Cognitive measures include RMT overall accuracy, SOT absolute angular direction error, SOT absolute distance estimate error, DMT discriminability (d'), and DMT response criterion (c). Affective measures include STAI-S scores, and we will use a mixed ANOVA to assess the effect of CES Group (2: Active, Sham), Session (2: Baseline, Follow-up), and Time (pre-task, 0-min, 20-min, 40-min, 60-min post-task).

Mixed ANOVAs will be conducted using package *rstatix* (ver. 0.7.0; Kassambara, 2023) in R (ver. 4.1.2). Mixed ANOVA assumptions will be checked using package *rstatix* (ver. 0.7.0; Kassambara, 2023) in R (ver. 4.1.2). Extreme outliers will be identified, removed, and mean imputed. Normality will be assessed with Shapiro-Wilk Normality Test; non-normal data will be log-transformed. Homogeneity of variance will be assessed with Levene's Test and confirmed all groups had the same or similar variance. Mauchly's test of sphericity will be automatically conducted and corrected for in the mixed ANOVAs analysis.

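### Section 5.2's N = 38 for 0.80 power matches a two-group comparison at one time point and is not tied to the SAP's mixed ANOVAs, whose power depends on correlations that neither document gives

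*Protocol*

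**What the plan says.** Protocol section 5.2 takes an effect size of f = 0.47 for subjective anxiety from an earlier CES trial and continues: "Using GPower, the total sample size was estimated to be 38 to achieve power of 0.80 with an alpha criterion of 0.05". It then sets the target: "Our goal is therefore 40 complete data sets, with 20 participants in each of the two groups". It does not name the GPower test family, the outcome, the model term, the number of measurements or a correlation among repeated measures. Nor does it say whether f refers to a difference at one time point, a change or an interaction.

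The Data Analysis part of Protocol section 6.0 plans GEEs and/or ANOVAs that cover "changes from baseline to follow-up, and changes due to Active versus Sham CES".

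The SAP is more specific about the models. For the physiological and biochemical outcomes, "we will use analysis of variance (ANOVA)s to assess the effect of CES Group (2: Active, Sham), Session (2: Baseline, Follow-up), and Time". Time has two levels (before and during stress) for HR, HRV, respiration and pupil diameter, and five levels for alpha amylase and cortisol. For the cognitive outcomes, "we will use mixed ANOVAs to assess the effect of CES Group (2: Active, Sham) and Session (2: Baseline, Follow-up" are the two factors. For STAI-S, "we will use a mixed ANOVA to assess the effect of CES Group (2: Active, Sham), Session (2: Baseline, Follow-up), and Time", with five Time levels. The SAP lists factors but does not say which main effect or interaction decides the treatment question, and it contains no power statement.

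**The concern.** Participants are randomised at scheduling and the Baseline stress test precedes every Active or Sham session, so a treatment effect can appear only at Follow-up. In a model with Group and Session, such an effect shows up as an interaction with Session. If the question is whether CES changes the response from before to during stress, it shows up as the three-way interaction with Time. The precision of both terms depends on how repeated measurements on one person correlate, and 5.2 says nothing about that.

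The stated 0.80 therefore cannot be carried over to the tests that will be run. The investigators' own previous study found no significant emotional, biochemical or physiological effect, so another null result is a live possibility. It would be read against a power of 0.80 that may or may not apply to the term tested.

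**Working it through.** **Inputs from the documents.** f = 0.47, alpha 0.05, power 0.80, N = 38 and a target of 40 (20 per group), all from Protocol 5.2. The expected 40-50% attrition is covered by enrolling up to 100 people, so 40 completers is the right N for this check.

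**Assumptions, because the documents give no values.** Two-sided test; equal SDs (set to 1); f read as a between-group difference at Follow-up only, so d = 2 x 0.47 = 0.94; correlations as stated below. Power is from the noncentral t with n per group and noncentrality (effect in SD units) x sqrt(n/2).

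**Step 1: reproduce 5.2.** One comparison of two groups at one time point, d = 0.94, df = N - 2:

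| N | Power |
|---|---|
| 36 | 0.782 |
| 38 | 0.805 |
| 40 | 0.826 |

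The smallest even N that reaches 0.80 is 38, exactly as stated.

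**Step 2: Group x Session, one value per session.** This is a t test on the change. With between-session correlation r, the change has variance 2(1 - r), so the standardised effect is 0.94 / sqrt(2(1 - r)). N = 40, df 38:

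| r | Effect | Power at 40 | N for 0.80 |
|---|---|---|---|
| 0 | 0.665 | 0.54 | 74 |
| 0.3 | 0.794 | 0.69 | 52 |
| 0.5 | 0.940 | 0.83 | 38 |
| 0.7 | 1.213 | 0.96 | 24 |

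Power at N = 40 crosses 0.80 at r of about 0.47. At r = 0.5 the change variance is 2 x 0.5 = 1, the same as a single measurement, so the required N is again 38.

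**Step 3: Group x Session x Time, two Time levels, effect only in the Follow-up during-stress cell.** The contrast is the difference between sessions in the pre-to-during difference. Let w be the correlation within a session, a the correlation across sessions at the same time level, and b the correlation across sessions at different time levels. Its variance is 4 - 4w - 4a + 4b.

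- Equal correlations (w = a = b = r): the variance is 4(1 - r). Power at N = 40 is 0.41, 0.54 and 0.75 at r = 0.3, 0.5 and 0.7; 0.80 needs r of about 0.73.
- Higher correlation within a session (w = 0.8, a = b = 0.5): the variance is 4 - 3.2 - 2 + 2 = 0.8, the standardised effect is 0.94 / sqrt(0.8) = 1.051, and power is 0.90.

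For five Time levels with equal correlations and the effect at one time point, power is 0.39, 0.53 and 0.78 at r = 0.3, 0.5 and 0.7, close to the two-level result.

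**Step 4: Follow-up adjusted for Baseline (ANCOVA).** The residual variance is 1 - r², so the standardised effect is 0.94 / sqrt(1 - r²). N = 40, df 37:

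| r | Effect | Power |
|---|---|---|
| 0 | 0.940 | 0.825 |
| 0.3 | 0.985 | 0.86 |
| 0.5 | 1.085 | 0.92 |

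**The case against.** The strongest reply is that 5.2's arithmetic is correct and nothing shows that the planned tests are underpowered. Several parts of this stand.

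- A reader might infer that 38 can come only from a one-way test. It cannot be pinned down that way. Group x Session with d = 0.94 at Follow-up and r = 0.5 also gives 38, as does GPower's Cohen effect-size option for a two-measure interaction; the SPSS option gives 40.
- A reader might infer that the three-way test always has larger variance and lower power. That follows from forcing all correlations to be equal. Samples minutes apart may correlate more strongly than sessions weeks apart, and Step 3 shows that power can then exceed 0.80.
- An effect confined to one cell is an unfavourable pattern. If CES shifted both Time levels at Follow-up, Group x Session averaged over the two would have power 0.93 at r = 0.3 and 0.98 at r = 0.5 (equal correlations).
- The units of f = 0.47 are unknown. Read as the interaction effect under GPower's default option (two measures, correlation 0.5), N = 12 would suffice and 40 would be ample.
- That the interactions are the deciding terms is inferred from the design; the SAP does not say so.

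These replies remove any claim of a demonstrated shortfall. They leave the gap itself in place: the same N = 38 is compatible with very different power for the tests in the SAP, and 5.2 does not let a reader tell which applies.

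**Conclusion.** The point holds as a gap between the power statement and the planned analysis, not as an arithmetic error. For Group x Session at N = 40, the stated 0.80 holds only if the between-session correlation is about 0.47 or more. For Group x Session x Time it depends on both within-session and cross-session correlations, and the cases worked here run from 0.41 to 0.90. All of these figures assume equal SDs and d = 0.94 at Follow-up only; the three-way figures also assume an effect confined to the stress period.

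A reader might go further and conclude that 40 participants are too few, or that the SAP's tests do not have 0.80 power. The documents support neither conclusion, because they give no correlations and no units for f. The point is still worth acting on, because a test that makes the stated power hold without a favourable correlation is available from data already planned.

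**What to change.** Preferred: in the SAP, make the treatment test for each outcome the Active versus Sham difference at Follow-up, adjusted for the same measure at Baseline (ANCOVA). No new data are needed. With 40 complete sets and d = 0.94, power is at least 0.82 at any non-negative r for an outcome analysed on its own level, so the 0.80 in 5.2 then stands. For a pre-to-during response score the same holds only if d = 0.94 is in SD units of that score, and 5.2 should say so.

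If the mixed-ANOVA interactions are kept as the treatment tests, rewrite 5.2 to name the outcome, the tested term and the effect-size convention, and give power at N = 40 over a stated range of within-session and cross-session correlations.

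Leave N at 40 in either case. The cost is a rewritten paragraph in 5.2, plus a change of model in the SAP if ANCOVA is adopted. If the interactions are kept, the stated power may be less favourable than 0.80.

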Soldiers are continually exposed to acute stressors during training and operations, activating a cascade of biochemical changes in the body, including an initial sympathetic-adrenal medulla (SAM) catecholamine-related response, and a slower-moving hypothalamic-pituitary-adrenal (HPA) glucocorticoid-related response (Angelova et al., 2021; Axelrod & Reisine, 1984; Buchheim et al., 2019; Charmandari et al., 2005; Gagnon & Wagner, 2016; McEwen, 2007; Padgett & Glaser, 2003). The diverse effects of acute stress on neurotransmitters and the central nervous system are associated with similarly diverse perceptual and cognitive effects, generally related to the intensity of experienced stress and the processes demanded by specific mental tasks. For example, mild-to-moderate acute stress can improve performance on relatively basic (or well-learned and rehearsed) perceptual and cognitive tasks, such as simple reaction time and verbal memory retrieval, perhaps owing to activation of the ascending reticular activating system (ARAS) (Arnsten, 2009; Broadbent, 1971; Brunyé et al., 2021a, 2021b; De Cicco et al., 2018; Hupbach & Fieman, 2012; Shields et al., 2019). Moderate-to-high acute stress, in contrast, can negatively influence performance on tasks more demanding of executive processes and spatial memory retrieval, perhaps owing to HPA-related activation and brain regions (e.g., prefrontal cortex, hippocampus) with high glucocorticoid receptor densities (Arnsten, 1998, 2009; Brunyé et al., 2016, 2019; Cerqueira et al., 2007; Luine et al., 1994; Olver et al., 2015; Richardson & VanderKaay Tomasulo, 2011; Shields et al., 2015, 2016).

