1. Two extant research studies suggest that 300 μ A (Bystritsky et al., 2008; Overcash et al., 1989) and up to 1500 μ A (Smith et al., 1994) are effective at lowering anxiety, in line with the conclusions of a review examining CES effects on anxiety and stress (De Felice, 1997).
2. Most of the data from our prior research with the device shows the predicted pattern of results, for example lower heart rate variability and respiration rate with CES (vs sham); however, the pattern is numerical only and does not reach traditional significance levels. We believe that higher intensity CES may

amplify these previously noted patterns; of course, this is an empirical question and cannot be answered without additional data collection.

3. This procedure of individualized thresholding is congruent with manufacturer's recommendations, and they report seeing the most reliable anxiolytic-like effects with this procedure. Also, the procedure of individualized thresholding and minimum intensity ($\geq 250\mu\text{A}$) is congruent with the Special Operations Command's (SOCOM) current use of the device during military training and operations, where they report anecdotal success for stress mitigation.

Second, rather than a single 20-minute session of CES administration, we will use daily administration (20-minutes/day) over the course of 4-6 weeks.

These first two modifications are being made to better conform with the device manufacturer's (Electromedical Products International, Inc., Mineral Wells, TX) recommendations for CES administration.

Finally, to elicit a more robust stress response that activates both SAM and HPA activity, we will increase the intensity (to level 3 of 5) of our torso shock administration. With these changes, we make four primary hypotheses:

H1: Biochemistry: We hypothesize that Active vs Sham CES will reduce biochemical responses to stress, including salivary alpha amylase as an indicator of SAM activity and salivary cortisol as an indicator of HPA activity.

H2: Physiology: We hypothesize that Active vs Sham CES will reduce physiological responses to stress, including heart rate, heart rate variability, respiration rate, and pupil diameter.

H3: Emotion: We hypothesize that Active vs Sham CES will reduce subjective experiences of stress, including responses on the STAI.

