1. Active or Sham CES Administration: Participants will be asked to continue sitting and relaxing in the chair and the electrode cable (still attached to their earlobes) will be connected to a different CES device. Two types of CES devices will be used: an Active device or a Sham device. The Sham devices are manufactured by EPII and look and behave exactly like the Active devices, however they do not actually send any electrical current to the electrodes. The two versions of the devices will be coded as devices A and B, and neither the experimenter nor participant will know which is Active and which is Sham; only the Principal Investigator will keep the key to decode whether the device is Active or Sham, to be revealed only during data analysis (or to a medical professional if there is an adverse event). The experimenters and participants will only know which coded device (device A or B) to use during CES sessions. In both conditions, the device will be powered on and set to the intensity identified during the CES Individualized Thresholding phase, and a countdown timer (displayed on the device screen) will begin.

After the 20 minutes of stimulation have elapsed, the device will automatically turn off. Immediately after the 20-minute CES administration, participants will complete the STAI-S questionnaire a second time, and the CES side effects questionnaire.

2. CES Secondary Administration: If a participant answer is ≥ 3 to one or more questions on the CES side effects questionnaire (in *both* the “presence and intensity” and the “relation to stimulation” sections), we will follow the manufacturer’s guidelines to administer additional CES until symptoms subside. According to the manufacturer’s internal research (derived from an analysis of over 10,000 CES sessions), brief secondary CES administrations can help

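### Four unranked primary hypotheses are tested on 12 listed outcomes at p<0.05 each, with no decisive outcome or term and no correction across outcomes, while Section 5.2 sizes a single test

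*Protocol*

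**What the plan says.** Section 5.2 rests on one published effect on subjective anxiety, f = 0.47, and concludes that "the total sample size was estimated to be 38 to achieve power of 0.80 with an alpha criterion of 0.05". The target is 40 complete data sets, 20 per group. The G*Power test is not named.

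In Section 2.0, under The Present Study, the protocol says "we make four primary hypotheses" and does not rank them. H1 is that "Active vs Sham CES will reduce biochemical responses to stress", through alpha amylase (AA) and cortisol. H2 covers heart rate, heart rate variability, respiration rate and pupil diameter. H3 covers the STAI. H4 expects "increased performance on tasks typically degraded by stress exposure, including a recognition memory test and a spatial memory test".

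The SAP fits a separate ANOVA to each of six physiological or biochemical outcomes, to the cognitive outcomes (it says four but lists five) and to STAI-S. Every model has Group and Session; seven also have Time.

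The Data Analysis part of Section 6.0 gives the decision rule: "An effect will be deemed statistically significant if the likelihood of its occurrence by chance is" below 0.05. It adds that "any follow-up comparisons (e.g., t-tests) will use a Bonferroni-corrected alpha criterion". The SAP has no multiplicity rule. Section 6.0 also directs the analysis to change from baseline to follow-up and to Active versus Sham differences.

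**The concern.** A 5% alpha and 0.80 power belong to one test of one outcome. The plan runs at least one Group test on each of 12 outcomes and treats each as significant at 0.05. Three of the four primary hypotheses have more than one outcome, and nothing says whether one significant outcome is enough or all are needed. Within each model, several terms contain Group. The text in Section 6.0 makes the Group terms that include Session the evident target, but on the seven outcomes with Time there are two of these, Group x Session and Group x Session x Time, and no term is named as decisive.

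At stake is how the result is read. A claim for CES could rest on any of the 12 outcomes, and a mixed pattern would have no pre-stated interpretation. The protocol's Background reports such a pattern in the team's previous study: no significant emotional, biochemical or physiological effect, one cognitive gain and one cognitive loss.

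**Working it through.** **1. The plan's own figure.** Inputs from Section 5.2: f = 0.47, alpha 0.05, N = 38. For two groups d = 2 x 0.47 = 0.94. With noncentral F, lambda = f² x N = 0.2209 x 38 = 8.39 on 1 and 36 df, power is 0.805; at N = 37 it is 0.794. So 38 reproduces as a single 1-df test, and N = 40 gives 0.826. A 1-df test with one covariate (0.804 at N = 38) or in a four-cell layout (0.804) also gives 38, so N does not identify which test was meant.

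**2. Outcome count, from the hypotheses and the SAP lists.**
- H1: AA, cortisol = 2.
- H2: heart rate, heart rate variability, respiration rate, pupil diameter = 4.
- H3: STAI-S = 1.
- H4: recognition accuracy, spatial direction error, spatial distance error = 3; or 5 with the two decision-making (DMT) measures, which the wording of H4 neither includes nor excludes.
- Total listed: 2 + 4 + 1 + 5 = 12 (11 by the SAP's own count of four cognitive measures).

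**3. Chance of at least one p<0.05 with no true effect, one Group term per outcome.** If independent, 1 - 0.95^k. If correlated, integration over equicorrelated normal test statistics. The documents give no between-outcome correlations, so these are assumed.

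| Set | k | Independent | Correlation 0.5 |
|---|---|---|---|
| H1 | 2 | 1 - 0.95² = 9.8% | 9.1% |
| H2 | 4 | 1 - 0.95⁴ = 18.6% (0.1855) | 15.6% |
| H4, without DMT | 3 | 14.3% | 12.5% |
| H4, with DMT | 5 | 22.6% | 18.3% |
| All listed | 12 | 46.0% | 31.9% |

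For all 12, correlation 0.7 gives 23.2% and 0.9 gives 13.5%. Letting a second Group term count on any outcome can only raise these figures.

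**4. Error under the proposed rule.** Four tests, the first Holm step at 0.05/4 = 0.0125: 4.9%, 4.3% and 2.6% at correlation 0, 0.5 and 0.9.

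**5. Power with 20 per arm, if d = 0.94 is a follow-up difference.** Let r be the baseline to follow-up correlation, which the documents do not give. Noncentrality is d_eff x sqrt(20/2). For Group x Session, d_eff = 0.94/sqrt(2(1 - r)) with 38 df. For ANCOVA, d_eff = 0.94/sqrt(1 - r²) with 37 df. Example at r = 0.2: 0.94/sqrt(1.6) = 0.743 against 0.94/sqrt(0.96) = 0.959.

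| r | Group x Session, 0.05 | ANCOVA, 0.05 | ANCOVA, 0.0125 |
|---|---|---|---|
| 0.2 | 0.63 | 0.84 | 0.66 |
| 0.3 | 0.69 | 0.86 | 0.69 |
| 0.5 | 0.83 | 0.92 | 0.785 |
| 0.7 | 0.96 | 0.98 | 0.93 |

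Without baseline adjustment, power at 0.0125 is 0.64. The difference detectable with 0.80 power is d = 0.91 at alpha 0.05 and d = 1.10 at 0.0125.

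**The case against.** **The plan does correct for multiplicity.** It does so for follow-up comparisons. That governs tests made after an ANOVA effect is found within one outcome; it leaves the ANOVAs on separate outcomes untouched.

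**H1 to H4 are separate claims, so error per hypothesis is the right measure.** This is defensible, and on that view the relevant range is 9% to 23% rather than the 12-outcome figure. It still exceeds 5% for H1, H2 and H4. H3 has one outcome but no named term.

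**The intended contrast is clear.** In part: Section 6.0 points to Group terms with Session. It does not choose between the two-way and three-way terms.

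A reader might also infer four stronger things that the documents do not support.

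- *That the trial's false-positive rate is 46%.* That figure needs independent outcomes, and measures taken on the same people in the same session are probably correlated.
- *That Section 5.2 is wrong, or underpowered unless r is about 0.47 or more.* The number 38 reproduces. The threshold on r applies only if f = 0.47 is a difference at follow-up, and Section 5.2 does not say whether it describes a follow-up difference, a change or an interaction.
- *That f = 0.47 at least justifies H3.* The Background says that study treated participants with an anxiety disorder and rated them on a Hamilton anxiety scale. This trial excludes anxiety disorders and uses STAI-S around shock stress.
- *That one analysis is more powerful for AA, cortisol and STAI-S.* The Background describes "a slower-moving hypothalamic-pituitary-adrenal (HPA) glucocorticoid-related response", which might seem to favour the three-way term. But for a 0.8 SD reduction from 20 minutes on (alpha 0.0125, r = 0.3, within-session correlation 0.6, all assumed), ANCOVA on mean post-task minus pre-task against the three-way term gives 0.58 v 0.68 under one cross-session correlation structure and 0.50 v 0.47 under another. The ranking reverses, so none is claimed.

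**Conclusion.** The concern holds as a defect in the decision rule. The documents name no decisive outcome or term for any of four primary hypotheses and apply no correction across outcomes. Following the stated rule gives an error rate above 5% for every hypothesis with more than one outcome: 9% to 23% within H1, H2 and H4 at correlations of 0 to 0.5, and 13.5% to 46% across all 12 at correlations of 0.9 to 0. The direction does not depend on the assumed correlations short of perfect correlation; the size does. Both Group x Session and Group x Session x Time are valid tests, and the fault is that neither is chosen. The power comparison in step 5 is conditional on d = 0.94 being a follow-up difference and on r. This should be corrected, but it does not invalidate the design or the data.

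**What to change.** 1. **Decision rule.** In the SAP, name one outcome and one decisive test for each of H1 to H4, say whether the two decision-making measures belong to H4, apply Holm across the four, and label all other outcomes and terms secondary.
2. **Decisive test.** For single-value outcomes and for during-stress minus pre-stress responses, use ANCOVA of the Follow-up value on Group, adjusted for the same Baseline value. For AA, cortisol or STAI-S, pre-specify one summary or one interaction term, not both. A 4-df interaction has no sign, so if it is chosen, state how a reduction will be read from it.
3. **Section 5.2.** State that 0.80 power applies to one 1-df test at alpha 0.05, and give the detectable differences (d = 0.91 at 0.05 and 1.10 at 0.0125, before baseline adjustment). State the assumed r. Say that carrying f = 0.47 over to STAI-S under shock stress in healthy participants, or to H1, H2 and H4, is an assumption. In the SAP, correct the count of cognitive measures to five.

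**Timing.** Section 6.0 says "only the Principal Investigator will keep the key to decode whether the device is Active or Sham, to be revealed only during data analysis". These choices should be fixed before then. The documents do not show whether the key is still closed: the SAP's sentence on Levene's test mixes future and past tense, which is not evidence either way. If the key is open, report the choices as post hoc.

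**Cost.** SAP wording and one model per named outcome; no new data. The price is power: at d = 0.94 the first Holm step has 0.64 unadjusted, and with ANCOVA it stays below 0.80 at r of 0.5 or less.
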